10.1.6 Dose modifications and delay

10.1.6.1 Dose modifications for SHR-1210

Adverse events related to SHR-1210 may be immune-related (irAE), and may develop shortly after the first dose or months after the last dose. SHR-1210 should be interrupted if events listed in [Table 4](#) occur. During the study, the investigator must consult with the sponsor if, based on the benefit to risk ratio of the subject, SHR-1210 should be interrupted or resumed instead of the recommendations found in [Table 4](#) or when the situation is not listed.

When SHR-1210 is discontinued and apatinib is well tolerated, the subject may receive apatinib monotherapy.

Table 4. Criteria for SHR-1210 dose modifications

Treatment-Related Immune-Related Adverse Events (irAEs)	Severity Grades for Treatment Interruption	Resumption	Discontinuation
Diarrhea/Colitis	2-3	Recovered to Grade 0-1	Fail to resolve within 12 weeks from the last dose, or the dose of corticosteroids cannot be reduced to ≤ 10 mg of prednisone or equivalent within 12 weeks.
	4	Discontinuation	Discontinuation
AST, ALT, or bilirubin increased	2	Recovered to Grade 0-1	Fail to resolve within 12 weeks from the last dose.
	3-4	Discontinuation	Discontinuation
Hyperthyroidism	3	Recovered to Grade 0-1	Fail to resolve within 12 weeks from the last dose, or the dose of corticosteroids cannot be reduced to ≤ 10 mg of prednisone or equivalent within 12 weeks.
	4	Discontinuation	Discontinuation
Hypothyroidism	2-4	Treatment can be continued after starting thyroxine replacement therapy	Treatment can be continued after starting thyroxine replacement therapy

Treatment-Related Immune-Related Adverse Events (irAEs)	Severity Grades for Treatment Interruption	Resumption	Discontinuation
Pulmonitis	2	Recovered to Grade 0-1	Fail to resolve within 12 weeks from the last dose, or the dose of corticosteroids cannot be reduced to ≤ 10 mg of prednisone or equivalent within 12 weeks.
	3-4	Discontinuation	Discontinuation
Immune-Related Hypophysitis	2-3	Recovered to Grade 0-1; SHR-1210 treatment can be resumed after starting hormone replacement therapy	Fail to resolve within 12 weeks from the last dose, or the dose of corticosteroids cannot be reduced to ≤ 10 mg of prednisone or equivalent within 12 weeks.
	4	Discontinuation	Discontinuation

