Type I diabetes mellitus (new onset) or hyperglycemia	New-onset type I diabetes mellitus or Grade 3-4 hyperglycemia accompanied with evidence of β -cell depletion	After clinical and metabolic conditions are stabilized	Continue SHR-1210 treatment.
Renal Failure or Nephritis	2	Recovered to Grade 0-1	Fail to resolve within 12 weeks from the last dose, or the dose of corticosteroids cannot be reduced to ≤ 10 mg of prednisone or equivalent within 12 weeks.
	3-4	Discontinuation	Discontinuation
Infusion reactions	2	Symptoms disappeared	Re-administer at 50% of the initial rate after symptoms resolve. If no reaction occurs within 30 min, restore the original infusion rate (100%). Closely monitor. If the symptoms recur, the administration of the current SHR-1210 dose will be discontinued.
	3-4	Discontinuation	Discontinuation
Other Treatment-Related Adverse Events	3	Recovered to Grade 0-1	Fail to resolve within 12 weeks from the last dose, or the dose of corticosteroids cannot be reduced to ≤ 10 mg of prednisone or equivalent within 12 weeks.
	4	Discontinuation	Discontinuation

Note: Treatment should be discontinued if any Grade 3 treatment-related AE recurs or any life-threatening event occurs.

For subjects with metastasis to liver and Grade 2 AST or ALT increased at baseline, treatment should be discontinued if a $\geq 50\%$ increase in AST or ALT from baseline persists for at least 1 week.

For subjects with intolerable or persistent Grade 2 treatment-related AEs, the investigator may consider interrupting SHR-1210 treatment if appropriate. For subjects with persistent Grade 2 adverse drug reactions that fail to recover to Grade 0-1 within 12 weeks after the last dose, the treatment should be discontinued.

For subjects with hypertension with a blood pressure not more than 140/90 mmHg whose AE is considered as Grade 3-4 only because of the administration of multiple antihypertensive drugs, treatment interruption is not required.

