13.1.2 AE severity grading criteria

The severity of AEs will be graded as per NCI-CTCAE v4.03. Refer to the following criteria for AEs not listed in the table of NCI CTCAE v4.03:

Table 10. CTC-AE severity grading criteria

Grade	Clinical Description of Severity
1	Mild; asymptomatic or mild clinical symptoms; clinical or laboratory test abnormality only; intervention not indicated.
2	Moderate; minimal, local, or noninvasive intervention indicated; limiting age-appropriate instrumental activities of daily life, e.g., cooking, shopping, using the telephone, counting money, etc.
3	Severe or medically significant but not immediately life-threatening; leading to hospitalization or prolongation of hospitalization indicated; disabling; limiting self-care activities of daily living (ADL). Self-care ADL: refer to bathing, dressing and undressing, feeding self, using the toilet, taking medications, and not bedridden
4	Life-threatening consequences; urgent intervention indicated
5	Resulting in death

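### Table 4 and the note beneath it give opposite SHR-1210 instructions for recurrent Grade 3 or life-threatening events in the hypothyroidism and type I diabetes/hyperglycemia rows

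*Protocol*

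**What the plan says.** Protocol Section 10.1.6.1, Table 4, lists immune-related events by row, with columns for the grades that trigger interruption, the condition for resuming, and the condition for discontinuing SHR-1210.

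- **Hypothyroidism, Grades 2-4.** The resumption and discontinuation cells carry the same text: "Treatment can be continued after starting thyroxine replacement therapy".
- **Type I diabetes or hyperglycemia.** The trigger is "New-onset type I diabetes mellitus or Grade 3-4 hyperglycemia accompanied with evidence of" beta-cell depletion. The resumption cell reads "After clinical and metabolic conditions are stabilized" and the discontinuation cell reads "Continue SHR-1210 treatment".
- **Catch-all row**, "Other Treatment-Related Adverse Events". Grade 3 is interrupted until recovery to Grade 0-1; Grade 4 is discontinued.
- **Note under the table.** "Note: Treatment should be discontinued if any Grade 3 treatment-related AE recurs or any life-threatening event occurs".

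A later paragraph in the same set of notes exempts one situation from interruption: hypertension graded 3-4 solely because several drugs are needed to control it. No comparable exemption is given for the two rows above.

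Appendix 7.4 allows immunotherapy to go on with thyroid hormone replacement when thyroxine is reduced, and sets no upper grade. Section 13.2.1 defines a life-threatening event as one that puts the subject at immediate risk of death when it occurs.

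**The concern.** The note is written as a general rule for every event. The two rows answer the question of when to discontinue by telling the site to go on. Where an event meets both the row and the note, a site that follows one breaks the other.

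First, this is a safety matter: the conflict lies in the stopping rule for the investigational antibody, and it concerns the more serious presentations. Second, there is a smaller reporting consequence. The SAP summarizes SHR-1210 exposure and dose intensity (Section 5.5.1) and adverse events leading to treatment discontinuation (Section 5.5.2). If sites resolve the conflict differently, those summaries partly reflect how each site read the protocol. The same applies to controls who cross over, because Section 11.4.2 sends them to the visit content of the investigational treatment period and they receive the same antibody.

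**Working it through.** No arithmetic applies. The check sets each row against the note, by grade and circumstance, taking life-threatening in the sense of Section 13.2.1.

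| Event | Row in Table 4 | Note under Table 4 | Result |
|---|---|---|---|
| Hypothyroidism, life-threatening | Continue on replacement | Discontinue | Conflict |
| Hypothyroidism, treatment-related Grade 3, recurrent | Continue on replacement | Discontinue | Conflict |
| Hypothyroidism, first Grade 3, not life-threatening | Continue on replacement | Not triggered | None |
| Type I diabetes or hyperglycemia with beta-cell depletion, life-threatening | Resume after stabilization, then continue | Discontinue | Conflict |
| Hyperglycemia with beta-cell depletion, treatment-related Grade 3, recurrent | Resume after stabilization, then continue | Discontinue | Conflict |
| Hyperglycemia with beta-cell depletion, first Grade 3, not life-threatening | Resume after stabilization, then continue | Not triggered | None |
| Treatment-related hyperglycemia without beta-cell depletion, Grade 4 | Outside this row; catch-all row discontinues | Discontinue if life-threatening | None |

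Four of the seven situations conflict. Three places might have settled which instruction governs:

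1. **The notes themselves.** They contain an explicit exemption, for drug-controlled hypertension, but not for these rows.
2. **The consultation clause in Section 10.1.6.1.** It applies when the investigator wants to depart from Table 4 or meets a situation that is not listed. Here the situation is listed and the instructions disagree, so a site cannot tell which action is the departure.
3. **Appendix 7.4.** For thyroid events it agrees with the row and not with the note. It also tells the investigator to proceed according to the protocol, which leads back to Table 4. Its listed entries do not cover diabetes or hyperglycemia.

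Other endocrine rows show that no general exemption for replaceable hormones can be assumed. The hypophysitis row also allows hormone replacement, yet discontinues at Grade 4; so does the hyperthyroidism row.

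**The case against.** The strongest reply is that a specific row ordinarily governs over a general note. The intent looks deliberate: Table 4 separates hyperthyroidism from hypothyroidism, gives them different Grade 4 outcomes, and Appendix 7.4 repeats continuation on replacement. Equally, the rows do not mention recurrence, so the note might be read as adding to them. Either reading is reasonable, but they lead to opposite actions and the protocol states neither. The discontinuation cells of these two rows are also not silent; they say to continue.

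The objection does limit how far the point reaches. A reader might infer more than the documents support in three ways:

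- **That every Grade 4 event in these rows conflicts.** Table 10 describes Grade 4 as "Life-threatening consequences; urgent intervention indicated", but Section 13.1.2 uses that table only for events that CTCAE v4.03 does not list. The documents do not show that hypothyroidism or hyperglycemia is unlisted. Under Section 13.2.1 a Grade 4 event triggers the note only if there is immediate risk of death.
- **That all Grade 3-4 hyperglycemia may continue.** The row requires evidence of beta-cell depletion and allows resumption only after stabilization.
- **That the 12-week Grade 2 rule is a further contradiction.** That note begins "For subjects with persistent Grade 2 adverse drug reactions that fail to recover to Grade 0-1 within 12 weeks after the last dose". Its clock runs from the last dose. Once three-weekly dosing resumes on thyroxine, a 12-week gap, four cycles, would not ordinarily arise.

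**Conclusion.** The inconsistency stands in a narrow form. For a recurrent treatment-related Grade 3 event, or a life-threatening event, that falls in the hypothyroidism row or the type I diabetes/beta-cell-depletion row, the protocol both directs continuation and requires discontinuation, with no order of precedence. This assumes that the note, which stands in the SHR-1210 section, refers to SHR-1210 treatment.

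Its frequency cannot be stated. Section 5.3 lists hypothyroidism in 19.8% of 258 subjects. A reader might multiply this by the planned arm size, 292/2 = 146, to get 0.198 × 146 = 28.9, about 29 subjects. That does not measure the conflict. The rate is for any grade, the passage does not name the regimen of the 258 subjects, and nothing is given for recurrent Grade 3 or life-threatening cases, or for hyperglycemia. The true number may be far smaller.

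Alpha, power and sample size are unaffected. The primary endpoint counts progression whether or not treatment continues (Protocol Section 12.1; SAP Section 4.1.1.1). The case for acting rests on contradictory safety instructions and, secondarily, on the consistency of the exposure and discontinuation summaries. Differing site practice is a possible consequence; the documents do not show that it has occurred.

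**What to change.** Reconcile the note under Table 4 with the two rows and with Appendix 7.4. Either add a sentence to the notes stating that the hypothyroidism and type I diabetes/hyperglycemia rows are exceptions to the recurrent-Grade-3 rule, the life-threatening rule, or both; or amend the rows to match the note. The same sentence can point to Section 13.2.1 for the meaning of life-threatening. Which clinical rule applies is for the sponsor's clinical team; this review does not propose one.

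The cost is one sentence, or an edit to two rows, plus alignment of the thyroid entry in Appendix 7.4. No analysis, sample size or visit schedule changes.

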10.1.6.2 Treatment for Common Adverse Drug Reactions Related to SHR-1210

10.1.6.2.1 Immune-related adverse reactions

Adverse events caused by immuno-oncology (I-O) drugs are different from those of other anti-tumor drugs, especially in terms of severity and duration. SHR-1210 is one such drug, and therefore, early identification and management of adverse events is required to reduce the incidence of severe toxicities. The safety management procedures of similar approved drugs provide references to assist the investigator in assessing and dealing with adverse events involving the following systems: GI tract, kidneys, lungs, liver, endocrine, skin, and nervous system. Safety management rules for immuno-oncology drugs are presented in [Appendix 7. Management Principles for Immune Related Adverse Events](#).

10.1.6.2.2 Infusion reactions

During the course of this study, the investigator should pay close attention to potential infusion and/or allergic reactions, especially acute immune-mediated adverse reactions (including cytokine storms).

SHR-1210 is a fully humanized monoclonal antibody with little potential for infusion or allergic reactions, and thus, in general, no prophylactic medications are required prior to SHR-1210 infusion. Based on published relevant information, allergic reactions/events are most likely to occur within 24 h after infusion. If an allergic reaction/event occurs, the infusion should be slowed or interrupted based on the subject's condition, and supportive treatment should be given. In addition, prophylactics should be given before further administration. Possible allergic reactions include fever, chills, shiver, headache, rash, arthralgia, hypotension/hypertension, and bronchospasm.

Management of allergic reactions should be based on the medical practice and guidelines of the study center. The treatment recommendations for infusion reactions are shown below for reference.

Table 5. Treatment recommendations for infusion reactions related to SHR-1210

CTCAE Grade	Clinical Symptoms	Recommended Management	SHR-1210 Treatment
Grade 1	Mild and transient reactions	Bedside observation and close monitoring until recovery. Pre-dose prophylactics are recommended for subsequent administration: 50mg of diphenhydramine or equivalent, and/or 325-1000 mg of acetaminophen can be given at least 30 minutes before the administration of SHR-1210.	Continued use
Grade 2	Moderate reactions requiring treatment or interruption; rapidly resolve after symptomatic treatment (such as antihistamines, non-steroidal antiphlogistics, anesthetics, bronchodilators, intravenous fluids, etc.)	Intravenous administration of normal saline, 50 mg of diphenhydramine IV or equivalent and/or 325-1000 mg of acetaminophen; bedside observation and close monitoring should be given until recovery. Corticosteroids or bronchodilators can be considered based on clinical needs; The amount of study drug infused should be recorded in the original medical record; Pre-dose prophylactics are recommended for subsequent administration: 50mg of diphenhydramine or equivalent, and/or 325-1000 mg of acetaminophen can be given at least 30 minutes before the administration of SHR-1210. Corticosteroids (equivalent to 25 mg of hydrocortisone) can be used when necessary.	Interrupt. Re-administer at 50% of the initial rate after symptoms resolve. Restore the original infusion rate if no complications occur within 30 minutes. Closely monitor. If the symptoms recur, no more infusion shall be given.
Grade ≥ 3	Grade 3: Severe reaction without rapid recovery with treatment and/or interruption; or symptoms recur after alleviation; or the subject develops sequelae that requires hospitalization. Grade 4: Life-threatening.	Immediately discontinue SHR-1210; Administer normal saline by intravenous infusion. Bronchodilators are recommended. Subcutaneous injection of 0.2-1 mg of 1:1000 adrenaline solution or slow intravenous infusion of 0.1-0.25 mg of 1:10,000 adrenaline solution is recommended. Intravenous infusion of diphenhydramine 50 mg and methylprednisolone 100 mg (or equivalent dose) can be given if necessary. Medical practices and guidelines for treating allergic reactions at the study center are followed. Bedside observation and close monitoring until recovery.	Discontinuation

10.1.6.3 Apatinib Dose Modification

Dose modifications due to apatinib-related toxicity include: dose delay (for up to 28 days), dose reduction (first dose modification: 375 mg qd, second dose modification: 250 mg qd), and permanent treatment discontinuation.

In case of Grade ≥ 3 apatinib-related toxicity, administration should be delayed until recovery, and then the original dose should be resumed or the dose should be reduced by one dose level. The minimum dose allowable is 250 mg/d. If the dose is still intolerable at the reduced dose of 250 mg/d, apatinib should be permanently discontinued (refer to [Table 6](#) for the recommended dose modification method). When apatinib is discontinued and SHR-1210 is well tolerated, the subject may receive SHR-1210 monotherapy.

In case of Grade ≥ 3 AEs unrelated to apatinib, the investigator shall decide on dose delay based on the actual situation.

If apatinib causes Grade 2 ALT or AST increased for ≥ 7 days, the investigator can interrupt the apatinib treatment as appropriate.

Dose increase of apatinib is not allowed during the study period.

For subjects with hypertension with a blood pressure not more than 140/90 mmHg whose AE is considered as Grade 3-4 only because of the administration of multiple antihypertensive drugs, treatment interruption is not required.

Table 6. Recommended dose modification of apatinib

Apatinib Treatment-related toxicity	Grade	Dose delay	Criteria for resuming	Dose Modification Method	Criteria for Discontinuation
Hematologic Toxicity	Grade 1-2	No	—	—	—
	Grade 3-4	Yes	Toxicity returns to Grade ≤ 2	At the original dose or at a reduced dose level	Apatinib interruption for more than 28 days
Non-Hematologic Toxicity	Grade 1-2	No	—	—	—
	Grade 3-4	Yes	Toxicity returns to Grade ≤ 1	At the original dose or at a reduced dose level	Apatinib interruption for more than 28 days

10.1.6.4 Dose modification of doxorubicin/ifosfamide

For subjects receiving doxorubicin combined with ifosfamide, dose modification can be made based on toxicities.

Table 7. Recommended dose modification of doxorubicin/ifosfamide

Chemotherapy-related toxicity	Grade	Dose delay	Criteria for resuming	Dose Modification Method	Criteria for Discontinuation
Hematologic Toxicity	Grade 1-2	No	—	—	—
	Grade 3-4	Yes	Toxicity returns to Grade ≤ 1	At the original dose or at a reduced dose level	Chemotherapy interruption for more than 6 weeks
Non-Hematologic Toxicity	Grade 1-2	No	—	—	—
	Grade 3-4	Yes	Toxicity returns to Grade ≤ 1	At the original dose or at a reduced dose level	Chemotherapy interruption for more than 6 weeks

For non-severe or non-fatal toxicities (e.g., alopecia, appetite change and nail discoloration), dose modification may not be necessary as judged by the investigator.

Dose modification caused by toxicities of a single drug in the combination therapy will not affect the usage of other drugs according to the plan.

For subjects with hypertension with a blood pressure not more than 140/90 mmHg whose AE is considered as Grade 3-4 only because of the administration of multiple antihypertensive drugs, treatment interruption is not required.

Table 8. Dose modification of doxorubicin/ifosfamide

Drug	Initial Dose	Next Dose (85% of the initial dose)	Dose after the Next Dose
Doxorubicin	60 mg/m ² , q3w	51 mg/m ² , q3w	Discontinuation
Ifosfamide	2 g/m ² on D1-D4 q3w for combined medication or 2 g/m ² on D1-D5 q3w for monotherapy	1.7 g/m ² on D1-D4 q3w for combined medication or 1.7 g/m ² on D1-D4 q3w for monotherapy	Discontinuation

Chemotherapy-related toxicities cannot resolve within the same treatment cycle. Thus, the administration of doxorubicin/ifosfamide can be delayed for no more than 6 weeks (± 3 days). If the toxicities still do not resolve by 6 weeks, the chemotherapy will be discontinued, unless the investigator considers that the subjects can benefit from continued chemotherapy.

10.2 Drug Management, Dispensation and Return

The management, dispensation, and retrieval of study drugs should be the responsibility of designated study staff. The investigator must ensure that all study drugs are used for subjects participating in this clinical study. The dosage and administration are shown in Section 10.1.5. Remaining or expired drugs should be returned to the sponsor and may not be used for non-participants.

When the drug is transported to the sub-center, a drug receipt form shall be signed in duplicate, one copy for the study center and one copy for the sponsor. When returning remaining drugs and empty packaging, both parties must sign the drug retrieval form. The dispensation and return of every drug should be immediately documented on designated forms.

The CRA is responsible for monitoring the supply, use, and storage of study drugs, and disposal of remaining medications.

10.2.1 Disposal of study drugs

The sponsor or his/her authorized personnel will provide guidance on the destruction of unused study drugs. If the study center is authorized to destroy the study drugs, the investigator must ensure that the destruction of the study drugs complies with applicable environmental regulations and company policies, and provide relevant procedures for destruction. The investigator should record all destruction activities.

10.3 Concomitant Medications

Concomitant medications refer to any drugs/treatments that are given for the interest of subjects as determined by the investigator.

All concomitant medications, blood products, and non-drug interventions (e.g., paracentesis) that are given to the subjects from 28 days prior to the first dose to the end of the safety visit must be strictly documented in the CRF according to GCP requirements. If a subject starts a new anti-tumor therapy during the safety follow-up period, only concomitant medications used for treatment-related AEs will be collected.

Prohibited medications and vaccines specified in the study protocol are strictly prohibited during the entire course of study. If the subject develops a comorbidity requiring treatment with a prohibited drug, the investigator should consult with the sponsor before discontinuing the study treatment or using the prohibited drug. Whether the subject will continue the study treatment or receive a prohibited drug should be jointly decided by the investigator, the sponsor, and the subject.

In addition to the following contents, for subjects who receive apatinib, doxorubicin, and ifosfamide, the latest package insert of marketed drugs or medical practices regarding contraindications and precautions shall also be taken for reference.

